3.4 Correlative studies

Investigational blood samples will be obtained on the first day of cycles 1 through 4. Any specimens not consumed by the analyses in this protocol will be banked for future research in the Cancer Research Specimen Bank (OHSU IRB 2816). See Appendix 7 for details.

3.5 End of Treatment Cycles

Patients who progress radiographically on ipilimumab after completion of the initial four doses will not receive more immunotherapy once progression has been documented. For soft-tissue lesions, the RECIST criteria for progression (see 6.4.2) will be used. For bone lesions, there should be ≥ 2 new lesions confirmed on a second scan at least 4 weeks later. Progression will not be assessed until completion of the initial 4 cycles of treatment in order to avoid premature discontinuation of therapy.

3.6 Follow-up visits after completion of ipilimumab therapy

Patients will be followed with a history, physical exam, CT and NM bone scan and serum PSA quarterly along with treatment visits during the maintenance treatment phase, until radiographic progression. If a patient has not met radiographic progression by Week 60 visit, the patient will be followed by PSA and scans until radiographic progression. Following radiographic progression, patients will be followed by semi-annual phone surveys with the patient, his family, or his treating physician to collect data on treatment status and overall survival for up to 5 years after all protocol treatment has been completed.

4 SUBJECT SELECTION CRITERIA

For entry into the study, the following criteria MUST be met. Any exceptions from the protocol-specific selection criteria must be approved by the Principal Investigator and/or the Institutional Review Board (IRB) before enrollment.

4.1 Inclusion Criteria

- 1) Willing and able to give written informed consent.
- 2) Histologic diagnosis of adenocarcinoma of the prostate.
- 3) A PSA of > 0.2 ng/ml after 6-18 months of androgen suppression therapy, which may consist of LHRH agonist or antagonist alone or the combination of an LHRH agonist or antagonist plus an antiandrogen, such as bicalutamide. Androgen suppression therapy will continue without interruption.
- 4) Radiographic evidence of regional or distant metastasis at the time of study enrollment or at the time of diagnosis.
- 5) Required values for initial laboratory tests:

• WBC $\geq 2000/\text{uL}$

• ANC $\geq 1000/\text{uL}$

• Platelets $\geq 50 \times 10^3/\text{uL}$

• Hemoglobin $\geq 8 \text{ g/dL}$

• Creatinine $\leq 3.0 \text{ x ULN}$

• AST/ALT $\leq 2.5 \text{ x ULN}$ for patients without liver metastasis

• Bilirubin $\leq 3.0 \text{ x ULN}$, (except patients with Gilbert's Syndrome, who must have a total bilirubin less than 3.0 mg/dL)

- 6) No known active or chronic infection with HIV, Hepatitis B, or Hepatitis C. Patients should be assessed for high risk behaviors that may result in these infections, such as intravenous drug use or multiple sexual partners. The assessment should be noted.
- 7) ECOG ≤ 1 .
- 8) Men \geq 18 years of age.
- 9) Patients receiving any herbal product known to decrease PSA levels (i.e. saw palmetto and PC-SPES), or any immunosuppressive dose of systemic or absorbable topical corticosteroid (except prednisone up to 10 mg orally q day, or its equivalent), must discontinue the agent for at least 2 weeks prior to screening. Progressive disease must be documented after discontinuation of these products.
- 10) Patients receiving bisphosphonate therapy must have been on stable doses for at least 4 weeks with stable symptoms prior to the first infusion with ipilimumab.

- 11) Total testosterone < 50 ng/ml, except in patients with prior orchiectomy, where testosterone does not need to be measured. Patients must continue their LHRH agonist therapy throughout study duration.
- 12) Life expectancy \geq 6 months. This must be documented.
- 13) Patients who are sexually active with a partner who could become pregnant are to use an effective form of barrier contraception, such as condoms or a partner using oral contraceptive pills. Persons of reproductive potential must agree to use an adequate method of contraception throughout treatment and for at least 8 weeks after ipilimumab is stopped.
- 14) If a patient enters the trial on AST that consists of both an LHRH agonist and an oral antiandrogen, both agents should be continued throughout the study. If an antiandrogen is stopped prior to study entry, it should be stopped 4 weeks before for nilutamide and flutamide and 6 weeks before for bicalutamide to ensure that a withdrawal phenomenon does not interfere with interpretation of efficacy results.

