N=30 (for the final analysis, 10 for the intial analysis). Using the Simon two-stage design for Phase II trials, the initial accrual will be 10 patients. Assuming that 10% of patients receiving usual care will achieve an undetectable PSA without additional intervention, the trial has a 80% power to detect a rate of achieving an undetectable PSA of \geq 30% among patients treated with ipilimumab. At least two patients with an undetectable PSA will be required in the first 10 patients to continue to stage 2. As soon as two patients achieve an undectable PSA, stage 2 for of the study will begin. If 6 or more of 30 patients have achieved an undetectable PSA at 6 months, the study will be considered successful and the regimen worthy of further investigation. This design has a type I error rate of 0.05 and a type II error rate of 0.20.

Demographic and clinical characteristics will be summarized using descriptive statistics (e.g. proportions, mean, standard deviation, median, range). The proportion of patients who achieve an undetectable PSA (≤0.2 ng/ml) after initiation of ipilimumab therapy will be provided with the exact 95% confidence interval. The Kaplan-Meier method will be used to estimate time to PSA progression, time to disease progression by any measure and time to death from any cause. In evaluation of time to PSA progression and time to disease progression by any measure will be censored for: (1) lost to follow-up at the date of last contact, (2) use of additional cancer therapies that would interfere with ascertainment of the endpoint of interest (3) death from causes other than prostate cancer or treatment of prostate cancer. Evaluation of time to death will be censored for lost to follow-up at last contact.

The effects of IRAEs and other immune parameters (e.g., a ratio of T regulatory cells to T effector cells) on clinical outcomes will be evaluated using logistic regression for binary endpoints (e.g., achievement of undetectable PSA) and Cox regression for the time to event outcomes (e.g., time to PSA progression).

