8.3 Sample Size Justification

N=30 (for the final analysis, 10 for the intial analysis). Using the Simon two-stage design for Phase II trials, the initial accrual will be 10 patients. Assuming that 10% of patients receiving usual care will achieve an undetectable PSA (PSA \leq 0.2) without additional intervention, the trial has a 80% power to detect a rate of achieving an undetectable PSA of \geq 30% among patients treated with ipilimumab. At least two patients with an undetectable PSA will be required in the first 10 patients to continue to stage 2. As soon as two patients having achieved an undectable PSA are identified, stage 2 for of the study will begin. If 6 or more of 30 patients have achieved an undetectable PSA at 6 months, the study will be considered successful and the regimen worthy of further investigation. This design has a type I error rate of 0.05 and a type II error rate of 0.20.

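### Eligibility can be read to admit men who added an antiandrogen shortly before entry, so a PSA fall caused by that drug could count as an ipilimumab success against a fixed 10% null

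*Combined protocol and SAP*

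**What the plan says.** Section 4.1, item 3 asks for "A PSA of > 0.2 ng/ml after 6-18 months of androgen suppression therapy, which may consist of LHRH agonist or antagonist alone", and the same sentence goes on to allow LHRH therapy plus an antiandrogen. The duration is attached to AST as a whole. The synopsis exclusion criteria also count time from the start of AST.

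Item 14 of section 4.1 says "If a patient enters the trial on AST that consists of both an LHRH agonist and an oral antiandrogen, both agents should be continued" for the whole study. It then deals with one kind of recent change: "If an antiandrogen is stopped prior to study entry, it should be stopped 4 weeks before for nilutamide and flutamide", with a longer period for bicalutamide, so that a withdrawal effect does not disturb the efficacy reading. Section 5.2.2 repeats both rules. Items 9 and 10 set a stop period for PSA-lowering herbal products and a stable-dose period for bisphosphonates. No section sets a minimum or stable period for an antiandrogen that has been started.

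The primary endpoint (sections 2.1 and 8.2) is a PSA of 0.2 or less at any time after ipilimumab begins. The benchmark in section 8.3 and the synopsis is "Assuming that 10% of patients receiving usual care will achieve an undetectable PSA without additional intervention". No source is cited, and neither usual care nor additional intervention is defined. Section 8.5 plans no analysis by antiandrogen start date.

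**The concern.** In a single-arm trial, every undetectable PSA is credited to the study drug, so the null rate must describe the men enrolled. Consider a man whose PSA stays above 0.2 after 12 months of LHRH therapy alone, who adds an antiandrogen, and who then enrols. He meets the wording of item 3, continues both drugs, and may reach 0.2 or less because of the antiandrogen. On the ordinary meaning of the words, he has had an additional intervention, and the 10% was not set for him.

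The protocol accepts that recent changes in PSA-active treatment can confound this endpoint, since it controls stopping an antiandrogen and the use of herbal products. It leaves starting an antiandrogen uncontrolled. A final cut-off of 6 successes in 30 is low enough for one or two misattributed responses to decide the trial.

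**Working it through.** **Inputs from section 8.3.** Null 0.10; target rate "30% among patients treated with ipilimumab"; "the initial accrual will be 10 patients", continuing if at least 2 succeed; success if at least 6 of 30 succeed; stated type I error 0.05 and power 0.80.

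**Step 1: reproduce the design.** P(success) = sum over x1 ≥ 2 of P(X1 = x1; n = 10, p) × P(X2 ≥ 6 − x1; n = 20, p).

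At p = 0.10:

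| x1 | P(X1 = x1) | P(X2 ≥ 6 − x1) | product |
|---|---|---|---|
| 2 | 0.19371 | 0.13295 | 0.02575 |
| 3 | 0.05740 | 0.32307 | 0.01854 |
| 4 | 0.01116 | 0.60825 | 0.00679 |
| 5 | 0.00149 | 0.87842 | 0.00131 |
| 6 or more | 0.00015 | 1 | 0.00015 |

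The sum is 0.0525, which matches the stated 0.05 to two decimals. At p = 0.30 the same formula gives 0.815, against a stated 0.80. The plan's figures reproduce, and the design has no slack under its own null.

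**Step 2: add men with a recently started antiandrogen.** Let m1 such men fall in stage 1 and m2 in stage 2. Each reaches 0.2 or less with probability q from the added drug, ipilimumab being inactive. All others stay at 0.10. Stage 1 successes are then Bin(10 − m1, 0.10) + Bin(m1, q), and stage 2 successes are Bin(20 − m2, 0.10) + Bin(m2, q). The decision rule is unchanged. The documents give neither the number of such men nor q, so both are assumptions.

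| Such men (stage 1, stage 2) | q = 0.20 | q = 0.30 |
|---|---|---|
| none | 0.0525 | 0.0525 |
| 1 (0, 1) | 0.058 | 0.063 |
| 1 (1, 0) | 0.062 | 0.072 |
| 3 (1, 2) | 0.075 | 0.102 |
| 6 (2, 4) | 0.103 | 0.173 |

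**Step 3: cost of counting such men as failures.** Set q = 0 for them and let everyone else respond at 0.30. With 3 such men (1 and 2 by stage), power falls from 0.81 to 0.74. With 6 (2 and 4), it falls to 0.64.

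**The case against.** The strongest counter-argument is about wording. Item 3 can be read as describing the treatment given during the 6-18 months, so that the qualifying PSA reflects failure on that same regimen. That reading is open. It is not stated, and the synopsis clock from the start of AST does not favour it. The point is therefore an ambiguity that permits the case, not a rule that plainly admits it.

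Some protections exist. Section 5.2.1 bars non-study anti-cancer agents during the study, which arguably covers an antiandrogen begun after consent, so the clear gap is a start before consent. Screening PSA must fall within 28 days of first treatment, AST is documented at screening and at treatment visits, and the lead site checks eligibility from source documents. These steps make a recent start visible but do not exclude it.

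The 10% is unsourced. Additional intervention could mean ipilimumab itself, or the 10% might already allow for routine AST changes. A reader might infer that the stated type I error of 0.05 no longer holds. The documents do not support that: they show neither that such men enrol nor what the 10% includes.

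A reader might also take a much larger bias from section 1.2, where 602 of 1,345 men (602/1345 = 44.8%) reached 0.2 or less. Those men were on initial AST. This trial enrols men who did not reach 0.2 on AST, so that rate is not a suitable anchor for adding a second hormonal drug.

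**Conclusion.** The concern holds as a gap in eligibility. Section 4.1, item 3 can be read to admit a man who recently added an antiandrogen. Item 14 and section 5.2.2 keep him on it and control only stopping, and the primary analysis would credit any resulting undetectable PSA to ipilimumab.

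The direction of the bias is clear: it favours declaring success. Its size is not known. One such man barely matters; six responding at an assumed 30% would more than triple the false-positive rate (0.173 against 0.0525). These figures assume that the 10% is right for everyone else and that it excludes added hormonal therapy. The sample size arithmetic is not in dispute. The gap is worth closing because there is no control arm to absorb it and the correction is cheap.

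**What to change.** Amend item 3 so that the PSA above 0.2 ng/ml is measured on the AST regimen the man carries into the study, with no AST component added between that PSA and dose 1. Extend item 14 and section 5.2.2 to a recently started antiandrogen, with a minimum interval between its start and the qualifying PSA. The sponsor should set that interval. Without it, a PSA drawn the day after the start would still qualify.

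Leave the existing antiandrogen-stop periods unchanged. Do not require the full 6-18 months on identical components: that would exclude men whom item 14 admits after stopping an antiandrogen and, with the 18-month limit, any man who adds one after month 12.

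Record the antiandrogen start date; AST is already documented under concurrent medications in section 6.1. In section 8.5, report the 6-of-30 result also with recent adders counted as non-responders. This is a conservative sensitivity analysis and does not replace the primary decision, because it discards true ipilimumab responses in these men (the power loss is shown in step 3 of the check).

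The cost is a short amendment and one extra data field. A few men would wait or be ineligible, and the sensitivity result can only be equal to or less favourable than the primary one.

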2 STUDY OBJECTIVES

2.1 Primary Objective

Proportion of patients who achieve an undetectable PSA (≤ 0.2 ng/ml) after initiation of Ipilimumab therapy.

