5.2.2 Restricted Therapies

If a patient enters the trial on AST that consists of a LHRH agonist and an oral antiandrogen, both agents should be continued throughout the study. Patients entering the trial may have stopped previous AST before starting this study for various reasons including but not limited to: AEs related to AST therapy, disease progression on AST, or at the discretion of the treating physician. If an antiandrogen is stopped prior to study entry, it should be stopped 4 weeks before for nilutamide and flutamide and 6 weeks before for bicalutamide to ensure that a withdrawal phenomenon does not interfere with interpretation of efficacy results.

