6 STUDY PROCEDURES AND OBSERVATIONS

6.1 Time and Events Schedule for Protocol CA184059

		Induction* (Cycles 1-4)			Between Treatments			Maintenance* (Cycles 5-8)			Every 6 Month Follow Up*		
T //P 1	Scree . #	Wk	Wk	Wk	Wk	Wk	Wk	Wk	11/1 24	WI 26	XX/1 40	W/I (0	Evel Fc
Test / Procedure	ning#	1	4	/	10	12	18	23/24	Wk 24	Wk 36	Wk 48	Wk 60	Π
Informed Consent	X												
Inclusion / Exclusion Criteria	X												
Demographics, medical history, concurrent medical conditions	X												
Testosterone level	X												
Serum samples for hepatitis panel and HIV, if high index of suspicion	X												
ECOG performance status	X	X	X	X	X	X	X	X	X	X	X	X	
Blood collection for correlative studies ¹		X	X	X	X								
Physical Exam	X	X	X	X	X	X	X	X	X	X	X	X	
Vital Signs	X	X	X	X	X	X	X	X	X	X	X	X	
Weight		X	X	X	X				X	X	X	X	
Bone Scan ²	X					X		X		X	X	X	
Chest, Abdomen & Pelvis CT ²	X					X		X		X	X	X	

CBC with differential	X	X	X	X	X	X	X	X	X	X	X	X	
Chemistry Panel: Creatinine, BUN, electrolytes (sodium, potassium, chloride), glucose, bilirubin alkaline phosphatase, ALT, AST, calcium, ³	X	X	X	X	X	X	X	Х	Х	X	Х	X	
LDH	X												
Autoimmune Profile: TSH, free T4	X	X	X	X	X				X	X	X	X	
PSA ⁴	X	X	X	X	X	X	X	X	X	X	X	X	
Concurrent medications (include documentation of androgen suppression therapy)	X	X	X	X	X				X	X	X	X	
Adverse Effects Recorded	X	X	X	X	X		_		X	X	X	X	
Ipilimumab		X	X	X	X				X	X	X	X	
Telephone Contact													X

^{*} Cycle 1-8 procedures can be done +/- 3 days and Long Term Follow-Up can be done +/- 2 weeks.

#Screening procedures must be done within 28 days of first treatment

^{**}PSA, Autoimmune profile, LDH, CBC Diff, Chem panel including Creatinine, BUN, electrolytes (sodium, potassium, chloride), glucose, bilirubin, alkaline phosphatase, ALT, AST, calcium, phosphorus and Correlative **baseline samples** DO NOT need to be repeated on Cycle 1 Day 1 if done within 7 Days of Cycle 1 Day 1

¹ Per outlined correlative studies

² Imaging Studies will also be done every three months until radiographic progression

³ Available labs (i.e. chemistries and blood counts) will be reviewed prior to each infusion

⁴ PSA will be done until radiographic progression

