8 STATISTICAL METHODOLOGY

8.1 Study Design

This is a single arm phase II trial.

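### As written, the testosterone limit in inclusion criterion 11 (50 ng/ml, or 5,000 ng/dl) excludes nobody, so it cannot verify androgen suppression; the effect on the primary result is of unknown size and direction.

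*Combined protocol and SAP*

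**What the plan says.** All references are to the combined protocol and SAP.

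- **Entry limit.** Section 4.1, item 11: "Total testosterone < 50 ng/ml, except in patients with prior orchiectomy, where testosterone does not need to be measured". The next sentence reads "Patients must continue their LHRH agonist therapy throughout study duration". No other section gives a testosterone limit or another unit for it.
- **AST requirement.** Section 4.1, item 3 asks for a PSA above 0.2 ng/ml after 6 to 18 months of AST and adds "Androgen suppression therapy will continue without interruption". Item 14 asks that a combined antiandrogen be continued.
- **A passage that pulls the other way.** Section 5.2.2: "Patients entering the trial may have stopped previous AST before starting this study".
- **Measurement.** The row "Testosterone level" in the section 6.1 schedule is marked at screening only, and section 3.1.2 lists the test among the screening laboratories.
- **Endpoint and benchmark.** The primary objective (section 2.1) is "Proportion of patients who achieve an undetectable PSA (≤ 0.2 ng/ml) after initiation of Ipilimumab therapy". Section 8.1 states "This is a single arm phase II trial", and section 8.3 sets the null by "Assuming that 10% of patients receiving usual care will achieve an undetectable PSA". The study continues past 10 patients with at least 2 responders and succeeds with at least 6 of 30.

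**The concern.** The purpose of item 11 can be read from its own wording. It is waived only after orchiectomy and is paired with the duty to stay on LHRH therapy, so it is there to confirm suppressed testosterone. A limit that every man meets confirms nothing.

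This matters because the trial asks what ipilimumab adds in men whose response to AST is incomplete. A PSA above 0.2 ng/ml can mean resistant disease or inadequate suppression, and only a testosterone value separates the two. There is no control arm. If an inadequately suppressed man later became suppressed and his PSA fell to 0.2 ng/ml or below, he would count as a treatment success. The protocol already guards against a related problem: items 14 and 5.2.2 set antiandrogen washout periods to protect the interpretation of efficacy.

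**Working it through.** **1. The unit.** 1 ng/ml = 100 ng/dl, so 50 ng/ml × 100 = 5,000 ng/dl. The same number in ng/dl would be 50 / 100 = 0.5 ng/ml, which is 100 times lower.

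**2. Whom the limit excludes.** The level in untreated men is an assumption, because the documents give none. The ratio of limit to level is:

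- at 2 ng/ml, 50 / 2 = 25
- at 15 ng/ml, 50 / 15 = 3.3
- at an extreme 30 ng/ml, 50 / 30 = 1.7

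The ratio stays above 1 throughout, so the limit excludes nobody. Read as 0.5 ng/ml, it would exclude every untreated man in the range.

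**3. Design baseline.** Inputs from section 8.3: at least 2 of 10 to continue, at least 6 of 30 to succeed, null rate 10%. With X₁ ~ Bin(10, 0.1) and X₂ ~ Bin(20, 0.1),

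P(success) = Σ over x ≥ 2 of P(X₁ = x) · P(X₂ ≥ 6 − x).

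- x = 2: 0.1937 × 0.1330 = 0.0258
- x = 3: 0.0574 × 0.3231 = 0.0185
- x = 4: 0.0112 × 0.6083 = 0.0068
- x = 5: 0.0015 × 0.8784 = 0.0013
- x ≥ 6: 0.0001

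The sum is 0.0525, against a stated 0.05. Power at 30% is 0.815, against a stated 0.80. The small excess over 0.05 belongs to the design and has nothing to do with testosterone.

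**4. Effect of k exposed men.** Suppose ipilimumab adds nothing. Of the 30 men, k are exposed and fall at random between the two stages. Each reaches PSA ≤ 0.2 ng/ml with probability q, and the other 30 − k do so with probability 0.10. Three values of q are used:

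- 0.20, chosen for illustration
- 0.448, which is 602/1,345, the share at or below 0.2 ng/ml in the cohort tabulated in section 1.2
- 1, the worst case

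Example for k = 1, q = 1. The man is in stage 1 with probability 10/30, which gives 0.1417, and in stage 2 with probability 20/30, which gives 0.1016. The weighted result is 0.0472 + 0.0677 = 0.1150 (unrounded terms).

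| Chance q per exposed man | k = 0 | k = 1 | k = 2 | k = 3 |
|---|---|---|---|---|
| 0.20 | 0.0525 | 0.0595 | 0.0670 | 0.0751 |
| 0.448 | 0.0525 | 0.0767 | 0.1079 | 0.1466 |
| 1 | 0.0525 | 0.1150 | 0.2249 | 0.3875 |

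**5. The other direction.** For k = 1 the result is linear in q. Extrapolating to q = 0, an exposed man who cannot reach the endpoint, gives 0.0595 − 0.2 × (0.1150 − 0.0595) / 0.8 = 0.0456. That is below 0.0525: such a man makes success less likely.

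**The case against.** A reader might infer that unsuppressed men can enter freely and that their PSA falls will be credited to ipilimumab. The documents do not support that.

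- **AST is still required.** Items 3, 11 and 14 demand 6 to 18 months of AST and its continuation. The section 6.1 schedule has AST documented with concurrent medications at screening and each dosing visit. Under section 3.2.1 eligibility is confirmed centrally from source documents before treatment. This stands. It narrows the exposed group but does not replace the criterion, since a record of AST shows exposure, not suppression. Section 5.2.2 also weakens the safeguard.
- **An upward bias needs a chain of events.** The man must be inadequately suppressed, become suppressed after entry, and then reach 0.2 ng/ml. Testosterone is not scheduled again after screening, so nothing in the plan prompts a correction. Section 5.2.1 bars non-study anti-cancer agents, which limits added hormonal treatment. If suppression stays poor, the man is plausibly less likely to respond, which counts against ipilimumab. The 10% null may also already absorb some late AST responses. All of this stands.
- **The largest figures are extreme.** The range 0.1150 to 0.3875 needs every exposed man to respond with certainty. The 44.8% is not a measured rate for this group either: it describes a whole cohort after 6 to 7 months of AST. The documents give no basis for any value of k. This stands too, which is why the results are shown as a range.
- **It is probably a slip of the pen.** Section 8.2 has a similar one, giving the PSA unit as ng/mg, and sites may apply a stricter limit in practice. That may be so, but item 11 is the operative text and nothing elsewhere corrects it.

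**Conclusion.** The point holds for the criterion itself. At 5,000 ng/dl it excludes nobody and cannot verify suppression. The one outside input is the testosterone level of untreated men, and the conclusion is the same from 2 to 15 ng/ml and even at 30 ng/ml.

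The consequence for the trial is a possibility, not a demonstrated bias. It is confined to men on AST who are inadequately suppressed, or who stopped AST before entry under a plain reading of section 5.2.2. Their number is unknown and the bias could go either way. For 1 to 3 men with some chance of a hormonal response, the false-success probability lies between 0.0595 and 0.1466 for the two moderate values of q, and reaches 0.3875 only in the worst case. The claim that the error rate is inflated by a known amount would go beyond the documents. The correction should still be made, because the criterion does not do its job and putting it right costs little.

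**What to change.** 1. The sponsor should confirm the intended unit of the limit in item 11 and correct the text. The eligibility checklist is not among the documents, so its unit should be checked against the corrected criterion.
2. Item 3 (AST uninterrupted) and section 5.2.2 (AST may have been stopped before entry) should be reconciled, so that it is clear what AST status is required at entry.
3. For men already enrolled, compare the screening testosterone on file with the confirmed limit, checking the unit in which each laboratory reported. Men exempt after orchiectomy have no required value and should not be counted as failing.
4. Keep the ITT population of section 8.4 for the primary analysis. Add a supplementary sensitivity analysis of the primary endpoint that leaves out men who fail the confirmed limit, given as a proportion with its exact 95% confidence interval. The 6-of-30 rule should not be applied to the smaller denominator.

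The cost is a short amendment, a review of results already on file and one extra table. No new test or visit is needed.
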